Study subjects will be recruited from November 2023 to May 2024 at Hung Vuong hospital, Ho Chi Minh city, Vietnam. Inclusion criteria for participants in this study include pregnant women who are 18 years old or older; who are indicated for laparoscopic surgery to treat ectopic pregnancy; and who agree to participate and provide a consent. Exclusion criteria include pregnant women who are allergic to anesthesia; who have hemodynamic instability; or who have ruptured ectopic pregnancies. The study is a parallel-group randomized control trial with 2 arms and no blinding. Arm 1 includes patients who will undergo single-port laparoscopy while aim 2 have patients undergo multi-port laparoscopy. All patients are randomized using computer-generated sequences with allocation ratio 1:1. Primary outcomes include blood loss, and surgical time. Secondary outcomes include pain intensity, surgical complications, hospital stay, and pneumoperitoneum. Blood loss and surgical time will be measured right after surgery while other outcomes will be measured during hospital stay. Technically, the investigators will perform examination 3-4 days post-surgery. Sampling will be stopped and the study will be concluded when patients are discharged from the hospital. The study design is visualized in Figure 1 below.

[figure not shown]

Figure 1: The CONSORT flow diagram of the study

Sample size calculation

The sample size is calculated based on the following formula:

$$n = \frac{(z_{1-\frac{\alpha}{2}} + z_{1-\beta})^2 [\sigma_1^2 + \frac{\sigma_2^2}{r}]}{\Delta^2}$$

$$r = \frac{n_1}{n_2}$$

$$\Delta = \mu_1 - \mu_2$$

Where:

n: required minimum sample size in each group

μ : outcome in each group

σ : standard deviation in each group

z: z score

α : type I error, $\alpha = 0,05$

β : type II error, $\beta = 0,15$ (statistical power = 0,85)

Based on Hsu-Dong Sun's group [1], sample sizes for each variable are as follows

Variables	4-port	1-port	Sample size
Bowel recovery time	$6,2 \pm 1$	$7,2 \pm 1,4$	24
Blood loss	$125 \pm 156,9$	335 ± 104	50
Visual analogue scale	$3 \pm 0,5$	$3,6 \pm 0,6$	14

The investigators anticipate to obtain the sample size of 50 for each group.

3. Aims and objectives

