The aim is to compare the effectiveness and safety of single-port versus traditional multi-port laparoscopic surgery in the treatment of ectopic pregnancy. Specifically, the surgical effectiveness will be evaluated via beta-hCG values, ultrasound imaging, and rate of switching to open surgery. The surgical safety will be evaluated via surgical time, blood loss, pain intensity, and surgical complications.

4. Outcomes

The primary outcomes of interest are the amount of blood loss during surgery, and surgical time. Secondary outcomes include pain intensity as indicated by visual analogue scale, surgical complications such as organ damages and surgical site infections, hospital stay, and pneumoperitoneum. The primary outcomes will be evaluated immediately post-surgery while the secondary outcomes will be evaluated within 4 weeks post-surgery by qualified practitioners.

5. Populations and subgroups to be analyzed

Populations: intention-to-treat

Subgroups: single-port versus multi-port group. These 2 subgroups will be analyzed using intention-to-treat populations.

6. Analyses

Data will be analyzed using Stata 16 (StataCorp LLC, College Station, TX). Normally distributed data will be expressed as mean \pm standard deviation, while non-normally distributed data will be shown as medians with interquartile ranges. T-test for normally distributed continuous variables and Mann-Whitney-U test for non-normally distributed continuous variables will be used to compare between groups. Categorical variables will be reported as absolute numbers and percentages; the Chi-square test or Fisher's exact test will be utilized for comparison. A *p*-value of <0.05 will be considered statistically significant.

7. References

- [1] Sun, Hsu-Dong, et al. "Comparison of single-port and three-port laparoscopic salpingectomy in the management for tubal pregnancy." *Journal of the Chinese Medical Association* 81.5 (2018): 469-474.

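### Two unranked primary outcomes are each tested at p<0.05 with no rule for a split result; if either one counts and neither truly differs, the false-positive chance is up to 10%.

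*Combined protocol and SAP*

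**What the plan says.** Section 2 (Study design) states: "Primary outcomes include blood loss, and surgical time". Section 4 (Outcomes) repeats the pair: "The primary outcomes of interest are the amount of blood loss during surgery, and surgical time". Neither section puts one ahead of the other.

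Section 6 (Analyses) assigns a t-test or a Mann-Whitney test to each continuous variable and then sets a single criterion for all comparisons: "A *p*-value of <0.05 will be considered statistically significant". Nothing in the combined document gives an order of testing, a split of alpha, or a one-or-both rule for the primary outcomes.

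The sample size calculation in Section 2 uses an undivided alpha of 0.05 and "statistical power = 0,85". Its table is introduced with "sample sizes for each variable are as follows" and has rows for bowel recovery time, blood loss and the visual analogue scale. There is no row for surgical time. The blood-loss row prints 50, and the section ends: "The investigators anticipate to obtain the sample size of 50 for each group".

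Section 3 (Aims and objectives) treats both primary outcomes as safety measures: "The surgical safety will be evaluated via surgical time, blood loss, pain intensity, and surgical complications".

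**The concern.** With two primary outcomes there are four possible patterns of significance. Two are easy to read: both significant, or neither. For the other two, the plan gives no interpretation. A trial that found a difference in blood loss but not in surgical time, or the reverse, could be reported as positive, negative or mixed, and each report would be consistent with the text. The trial is unblinded, so it is all the more useful to fix this choice in writing before the data are analysed.

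The error rate depends on which reading is chosen. If a significant result on either outcome is enough, there are two chances of a false-positive primary finding, each at 5%, and the rate for the pair exceeds 5% when neither outcome truly differs.

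**Working it through.** **Inputs from the documents.** Two primary outcomes (Sections 2 and 4). Threshold 0.05 per test (Section 6). Planning alpha 0.05, power 0.85 and 1:1 allocation (Section 2). Blood loss 125 with SD 156.9 for 4-port and 335 with SD 104 for 1-port, a difference of 210 (Section 2 table). Planned size 50 per group. I take the tests as two-sided, as the sample-size formula does; Section 6 does not say. The documents give no correlation between the two outcomes, so the correlations below are assumptions.

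**1. The plan's own figure.** With r = 1, the plan's formula for blood loss gives

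(1.960 + 1.0364)^2 x (156.9^2 + 104^2) / 210^2 = 8.978 x 35,433.61 / 44,100 = 7.2, so 8 per group.

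The table prints 50. The figure is not reproduced, so either the inputs or the 50 must be wrong. This does not affect the error rates in steps 2 to 4, which depend only on the threshold and the number of tests. It does affect the cost in step 5.

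**2. Either outcome suffices, neither truly differs.**

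- Independent tests: 1 - 0.95^2 = 0.0975.
- Any dependence: at most 0.05 + 0.05 = 0.10.
- Correlated test statistics (bivariate normal, absolute value above 1.96 on either):

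| Assumed correlation | Chance of at least one false positive |
|---|---|
| 0 | 0.0975 |
| 0.3 | 0.0951 |
| 0.5 | 0.0907 |
| 0.7 | 0.0835 |
| 0.9 | 0.0704 |
| 0.99 | 0.0566 |

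The limit at perfect correlation is 0.05.

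**3. Other readings.**

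- Both must be significant: at most 0.05.
- One outcome truly differs: only the other can be a false positive, at 0.05. The plan's blood-loss assumption (125 versus 335) is this case.

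**4. Under Holm.** The smaller p-value is compared with 0.025. If neither outcome differs, the error is 1 - 0.975^2 = 0.0494 for independent tests and at most 0.025 + 0.025 = 0.05 under any dependence. If one truly differs, it is also at most 0.05.

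**5. Power for blood loss at Holm's first step** (normal approximation; not computed for the Mann-Whitney test).

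- If the tabulated inputs are right: the standard error at 50 per group is sqrt(35,433.61 / 50) = 26.62, and 210 / 26.62 = 7.89. Power at 0.025 is Phi(7.89 - 2.2414), above 99.9%. The difference detectable with 85% power moves from 2.9964 x 26.62 = 79.8 to 3.2778 x 26.62 = 87.3.
- If 50 per group is the true requirement for 85% power at 0.05: power at 0.025 is Phi(1.960 + 1.0364 - 2.2414) = Phi(0.755) = 0.775. This is the lower bound, because blood loss is tested at 0.05 whenever surgical time has already passed 0.025.

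For surgical time, the plan gives no mean, SD or target difference, so no power can be computed.

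**The case against.** The strongest reply is that the plan never says either outcome is enough. Section 3 lists the two as separate safety measures. If each is reported as its own question, each test keeps its 5% error, and whether two such questions need adjustment is partly a matter of judgement. This stands to the extent that the defect is an omission. A reader might infer that the plan promises 5% for the pair and breaks that promise, or that the trial runs at a 10% false-positive rate. The documents support neither. Alpha appears in a formula applied variable by variable and in a threshold applied test by test, and the higher rate needs both an either-suffices reading and no true difference on either outcome.

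A second reply is that blood loss is in effect the lead outcome, since its printed 50 matches the chosen group size. That may be a hint, but no text says so. The same table sizes the visual analogue scale, which is secondary, and bowel recovery time, which is not among the listed outcomes, so having a row does not establish primacy.

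A third is that the plan expects a large blood-loss difference, in which case no inflation arises. This is correct under that assumption. Error control must also hold if the assumption is wrong, and a split result has no interpretation in either case.

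A fourth concerns the remedy. A stricter first step is less sensitive to harm on a safety measure, and the planning values have single-port losing more blood. Also, a p-value between 0.025 and 0.05 can fail Holm while the ordinary 95% interval excludes zero. Both points are fair, so the fix must say how intervals and tests are read together.

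**Conclusion.** The point holds as a gap that should be closed; it does not invalidate the trial. The certain part is that the plan does not say what a split primary result means. The conditional part is the error rate: 9.75% for independent tests, at most 10%, lower with correlation (9.1% at 0.5 and 7.0% at 0.9, both assumed values). It rests on either outcome being accepted as a positive primary result and on neither truly differing. Without both conditions the rate does not exceed 5%.

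A reader might also infer from the power above 99.9% that adjustment costs nothing. The documents do not support that without qualification, because the blood-loss inputs behind it give 8 per group and not 50, and surgical time has no inputs at all.

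**What to change.** Add to Section 6, before analysis:

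- The two primary outcomes are tested with the Holm procedure: the smaller p-value against 0.025 and, if that is significant, the larger against 0.05. Each outcome significant under this rule is a positive primary finding for that outcome.
- The effect estimate and 95% confidence interval are reported for both outcomes whatever the test result. Where the Mann-Whitney test is used, these are the Hodges-Lehmann median difference and its interval.
- These intervals are not adjusted for multiplicity. The Holm result decides the primary claim; the intervals are still used to judge possible harm.

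Holm works on p-values, so it applies with either test in the plan. An acceptable alternative is an explicit rule that both outcomes must be significant at 0.05 for a positive primary result. Its chance of success is at most the lower of the two powers: for example 0.85 x 0.85 = 0.72 if each has an assumed 85% and the tests are independent.

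The cost is one paragraph. For blood loss, power at 50 per group stays above 99.9% if the tabulated inputs are right, and is about 77.5% at Holm's first step if 50 is the true requirement for 85% power. The conflict between 8 and 50 should be resolved and the resulting power stated, rather than met by enrolling more patients. If blood loss passes first, surgical time is tested at the full 0.05 and loses nothing; otherwise its cost cannot be computed from the plan.
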